All safety endpoints will be summarized descriptively only within each of the 3 cohort separately. Adverse events will be further summarized by the values of infusion parameters within each cohort; rates per injection will be presented as well. Adverse events will be presented including a virtual System Organ Class comprising local reaction (identified by Medical Dictionary for Regulatory Activities high level terms: “administration site reactions NEC”, “infusion site reactions”, and “injection site reactions”) and by severity. Further, time to onset and duration will be presented descriptively. Tolerability of a certain infusion parameter within a cohort will be calculated as ‘number of infusions without severe local reaction / number of all infusions’ and be presented by infusion parameter and cohort.

Interim Analyses Not applicable.

Study Number:

IgPro20_4004

Study Product:

IgPro20

Schedule of Assessments – Pump-Assisted Flow Rate Cohort

Study Period	Screening	Forced Upward Titration																End of Study	
Study Day	-35 to -7	1	8	15	22	29	36	43	50	57	64	71	78	85	92	99	106	113±1 day	
Week Number		1 ^f	2	3	4	5 ^f	6	7	8	9 ^f	10	11	12	13 ^f	14	15	16	17 ^f	
Informed consent/assent	X																		
Inclusion / exclusion criteria	X	X																	
Medical history and demographics	X																		
Pregnancy test	X																		X
Physical examination	X																		X
Systolic and diastolic blood pressure, respiratory rate, pulse rate, and body temperature	X	X				X				X				X					X
Body weight and height	X																		X
Hematology ^a & biochemistry ^b	X																		X
Infusion training / supervised infusion / supervised entry of infusion data in the subject eDiary		X				X				X				X					
IgPro20 dispensation and IRT update		X				X				X				X					
Subject eDiary ^c training and review		X				X				X				X					X ^g
IgPro20 administration (weekly for pump-assisted infusions)		X	X	X	X	X	X	X	X	X	X	X	X	X	X	X	X	X	
Serum IgG trough level ^d		X																	X
Adverse events (including injection site assessments) ^e	X	X	X	X	X	X	X	X	X	X	X	X	X	X	X	X	X	X	X
Concomitant therapies	X	X				X				X				X					X

eDiary = electronic diary; IgG = immunoglobulin G; IgPro20 = Hizentra; IRT = Interactive Response Technology.

- a. Hematology: hemoglobin, hematocrit, mean corpuscular volume, erythrocytes, leukocytes, differential count, platelets.

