The benefits of manual push include the use of smaller volumes per infusion compared to less frequent infusion schedules. Other advantages associated with manual push include the ability to maintain more even serum IgG concentrations with higher trough levels compared to weekly or twice weekly schedules, which could potentially confer better protection against infections, as well as lower time per infusion and total time per weekly/monthly dose compared to pump-assisted infusions. The use of manual push is also associated with a simpler infusion technique (ie, there is no requirement to load and handle a pump) and reduced healthcare costs as there is no expenditure on a pump. The benefits of the higher flow rates and volumes, as proposed for the current study, include reduced infusion time, and fewer injection sites per infusion.

A number of disadvantages are associated with use of the manual push technique, including the difficulty to control the syringe to deliver a stable flow rate and the manual strength required to operate the syringe for several minutes.

Overall, the associated benefit-risk assessment of the study is considered acceptable for subjects enrolled in the study.

2. Study Objectives and Endpoints

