2.1.2 Primary Endpoints

The primary endpoints are as follows:

- Pump-Assisted Volume Cohort: Percentage of responders for each planned volume (ie, 25 mL, 40 mL and 50 mL per injection site).
- Pump-Assisted Flow Rate Cohort: Percentage of responders for each planned flow rate (ie, 25 mL/h, 50 mL/h, 75 mL/h and 100 mL/h per injection site).
- Manual Push Flow Rate Cohort: Percentage of responders for each planned flow rate (ie, 30 mL/h [0.5 mL/min], 60 mL/h [1 mL/min], and 120 mL/h [2 mL/min] per injection site).

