3.1 Study Design and Rationale

This multicenter, open-label, parallel-arm, non-randomized study is designed to evaluate safety and tolerability of higher infusion parameters of IgPro20 in subjects with PID. The study will include 3 cohorts with a minimum of 15 subjects each as follows:

- Pump-Assisted Volume Cohort (weekly infusions): Volume per injection site of 25 mL up to 50 mL.
- Pump-Assisted Flow Rate Cohort (weekly infusions): Flow rate per injection site of 25 mL/hour up to 100 mL/hour.
- Manual Push Flow Rate Cohort (2 to 7 infusions per week): Flow rate per injection site of 25 to 30 mL/hour up to 120 mL/hour (equivalent of approximately 0.5 mL/minute up to 2 mL/minute; see [Table 1](#)).

Each cohort will test 3 infusion parameter levels (for Pump-Assisted Flow Rate Cohort – 4) for at least 4 weeks each over a duration of 12 weeks (for Pump-Assisted Flow Rate Cohort – 16 weeks). After the fourth week on each level, qualifying subjects (responders) will switch to the next infusion parameter level (eg, from 25 to 50 mL/h). During the study the weekly dose will remain unchanged (as prescribed by treating healthcare provider, usually within 100-200 mg/kg per week range); only the respective infusion parameter under evaluation will change. If a subject is unable to tolerate the respective infusion parameter level (ie, is a non-responder at that level, for definition see [Section 11.3.5](#)), the subject will continue study

[figure not shown]
participation at the individually previously tolerated infusion parameter level for the remaining full study duration, to collect safety information.

If a subject within the Pump-Assisted Cohort is able to perform ≥ 3 out of 4 (75%) valid infusions at a certain infusion parameter level, he/she will be considered to be a responder for this infusion parameter level (eg, completed 3 infusions with 50 mL/h means responder for 50 mL/h). Valid infusions do not need to be consecutive. Determination of a responder in the Manual Push Cohort is more complex due to the expected variable frequency of infusions per week for different subjects (see [Section 11.3.5](#) for further details). Valid infusions in this cohort also do not need to be consecutive. However, each subject needs to adhere to the same schedule (number of infusions per week) throughout the study.

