4.1.1 Inclusion Criteria

Subjects meeting all of the following inclusion criteria may be enrolled into the study:

1. Capable of providing informed consent/assent and willing and able to adhere to all protocol requirements. The subject's parent(s) or legally acceptable representative(s) capable of providing written informed consent.
2. Male or female on stable dose of IgPro20 (Hizentra) therapy.
3. Women of childbearing potential must be using and agree to continue using medically approved contraception (which must be discussed with the study doctor) and must have a negative pregnancy test at Screening.
4. Subjects with PID, eg, with a diagnosis of common variable immunodeficiency or X-linked agammaglobulinemia, as defined by the Pan American Group for Immune

Deficiency and the European Society of Immune Deficiencies or by the International Union of Immunological Societies Expert Committee.

5. With infusion parameters as specified below:

Pump-Assisted Flow Rate Cohort subjects only*

5a. Experience with pump-assisted infusions of IgPro20 at the tolerated flow rate of 25 mL/h** per injection site for at least 1 month prior to Day 1.

Pump-Assisted Volume Cohort subjects only*

5b. Total weekly IgPro20 dose of ≥ 50 mL (≥ 10 g).

5c. Experience with pump-assisted infusions of IgPro20 at tolerated volumes of 25 mL/injection site for at least 1 month prior to Day 1.

Manual Push Flow Rate Cohort subjects only

5d. Experience with frequent (2-7 times per week) infusions of IgPro20 at the tolerated flow rate of approximately 0.5 mL/min (equivalent of 25-30 mL/h) per injection site for at least 1 month prior to Day 1. The dose (volume) per injection site should not exceed 25 mL.

*Subjects who tolerated higher infusion parameters relevant for their study cohort prior to the study based on their chart records will not be allowed to participate in the study. If records are not available, information may be obtained by asking the subject.

**Subjects who use an infusion pump that operates by maintaining a constant pressure as opposed to a constant flow rate, may not have experienced flow rates that are exactly 25 mL/h. Flow rates for constant pressure pumps (adjusted for needle gauge and infusion tubing size) that are within $\pm 20\%$ of 25 mL/h per injection site are acceptable for study entry.

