### 11.4 AEs

AEs starting on or after the date (and time if available) of the first administration of study treatment will be considered treatment-emergent AEs (TEAEs). This is the formal definition of a TEAE. It should be kept in mind that all subjects have been on a stable Hizentra® dose prior to study start.

When the AE start date is missing or partially missing, AEs will be assumed to be treatment-emergent, unless there is clear evidence (through comparison of partial dates) to suggest that the AE started prior to the first dose of study treatment. For the assignment of AEs within 72 hours after administration of treatment (temporally associated AEs), only AEs

with complete start dates will be considered. The start time will also be considered if available. AEs which start during infusion or within 72 hours after the end of an infusion will be considered temporally associated AEs.

Only TEAEs occurring until EOS visit will be included in the summary tables. All AEs will be listed.

For non-responder subjects at a certain infusion parameter level, AEs reported at the individually tolerable infusion parameter level after the non-response in the subject, i.e., AEs starting at or after the next infusion following the infusion leading to non-response, will be listed and flagged. These AEs will be analyzed separately from the AEs reported prior to that time.

AEs will be coded using the MedDRA version 20.0 or higher. AEs will be primarily classified by MedDRA PT. Analyses will be performed by SOC and PT. Aggregated incidences at SOC level and Any TEAE will also be provided.

Summaries of TEAEs will count the number of subjects, that is, subjects with multiple occurrences of the same PT will be counted once. Summaries of TEAEs will also include the number of events for each PT. Summaries will be presented for each infusion parameter and total within cohort. TEAEs will be assigned to the infusion parameter level under which they occurred. In the Total column within cohort, each subject will only be counted once with all events experienced.

AE rates per infusion will be calculated within cohort in the following way for each infusion parameter level:

- $$\text{AE Rate per Infusion} = \frac{\text{Number of Events for a Particular PT}}{\text{Number of Infusions}}$$

where number of infusions will be the sum of all infusions that subjects received within infusion parameter level irrespective of their validity as defined in Section 11.1.

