and will be presented by infusion parameter and cohort. The number of infusions irrespective of their validity as defined in Section 11.1 will be used as denominator for the assessment of tolerability. The total number of infusions within infusion parameter level and within cohort will be considered as denominator for the tolerability within infusion parameter level and within cohort, respectively. An infusion without severe local reactions is defined as no occurrence of a severe local reaction from the start date and time of an infusion until the start date and time of the next infusion or study end if this was the last infusion.

Local TEAEs will be identified by the MedDRA high level terms “administration site reactions NEC”, “infusion site reactions”, and “injection site reactions”. The MedDRA high level terms will be reviewed prior to database lock and the list of terms to be included into Local TEAEs will be updated. Local TEAEs will be included in all tables by using a virtual SOC called “Local Adverse Events”. In addition, the local TEAEs will also be presented by their MedDRA SOC “General disorders and administration site conditions”.

TEAEs will be sorted in descending order of total incidence by SOC and PT.

The summary will report for the Any TEAE row, each SOC, and each PT, the number of subjects with at least one TEAE, counted for the maximum reported severity in the table by severity. Local TEAEs will be reported only once in the Any row.

A listing of MedDRA SOC, PT, and verbatim text will be provided.

All AEs will be listed. TEAEs will be listed for the SAF. Other AE listings will use all available data. The listings will include the variables as specified in Section 7 and in addition MedDRA SOC, PT, and the verbatim, AE start and end date and time if available, duration of AE in days, severity, serious (yes or no), relationship to treatment (yes or no), outcome, action taken, and AE flags (TEAE, SAE, temporal relationship within 72h [AE72h]). Additionally, a listing of subject IDs for each individual PT will be produced.

The following listings will be provided:

- Non-TEAEs – all available data;
- TEAEs – SAF;
- Deaths – all available data;
- SAEs – all available data;
- AEs leading to study discontinuation – all available data;
- Local TEAEs – SAF;
- MedDRA SOC and PT with all AE verbatim – all available data;
- Subject IDs for each PT – all available data.

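### In the volume cohort, local-reaction rates per infusion should be accompanied by the number of injection sites and a per-site rate, because sites per infusion generally fall as volume per site rises

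*SAP*

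**What the plan says.** **Design.** Protocol 3.1 describes the cohort as "Pump-Assisted Volume Cohort (weekly infusions): Volume per injection site of 25 mL up to 50 mL" and says "During the study the weekly dose will remain unchanged". Inclusion criterion 5b requires a weekly volume of at least 50 mL and sets no upper limit. The levels are 25, 40 and 50 mL per site (Protocol 2.1.2). Protocol 1.4 lists the benefits of higher flow rates and volumes, which "include reduced infusion time, and fewer injection sites per infusion"; Protocol 1.1.4 makes the same point.

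**Analysis.** The secondary endpoints (Protocol 2.2.2) give local reactions per subject and per infusion, and tolerability as a percentage of infusions. SAP 11.4 follows them. The event rate has infusions as denominator, "where number of infusions will be the sum of all infusions that subjects received within infusion parameter level irrespective of their validity". For tolerability, "The number of infusions irrespective of their validity as defined in Section 11.1 will be used as denominator for the assessment of tolerability". Each AE table also gives the number and percentage of subjects and the number of events.

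**What is absent.** SAP 11.3 (exposure) does not summarise injection sites per infusion, and SAP 11.4 defines no rate per site.

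**Wording.** The synopsis says, of adverse events, that "rates per injection will be presented as well". Protocol 11.3.3 and SAP 11.4 speak of rates per infusion.

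**The concern.** The tested parameter is the volume delivered to one site, and a local reaction arises at a site. The unit in the denominator, the infusion, contains every site used that week. With the dose held constant, that unit generally holds fewer sites at the higher levels. A flat or falling per-infusion rate from 25 to 50 mL could therefore mean that volume per site makes no difference, or that a higher risk at each site is offset by having fewer of them. The planned tables cannot separate the two. Percentages of subjects do not help, because each subject also has fewer sites at the higher level. What is at stake is whether the trial can say that local reactions do, or do not, increase with volume per site.

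**Working it through.** **Plan's own figures.** The documents state no local-reaction rate, per infusion or per site, so there is none to reproduce. The sample-size figure of 94% does reproduce (5 or more responders of 15 at a true rate of 50%: 0.9408), but this point does not depend on it.

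**Inputs.** One infusion per week, so weekly volume V is the volume per infusion (Protocol 3.1); V of at least 50 mL (Protocol 4.1.1); levels L of 25, 40 and 50 mL per site (Protocol 2.1.2). Per-site risks are assumptions.

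**Step 1: minimum sites per infusion**, n(L) = V / L rounded up.

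| Weekly volume | 25 mL | 40 mL | 50 mL | n(25)/n(50) |
|---|---|---|---|---|
| 50 mL | 2 | 2 | 1 | 2.0 |
| 60 to 75 mL | 3 | 2 | 2 | 1.5 |
| 80 mL | 4 | 2 | 2 | 2.0 |
| 100 mL | 4 | 3 | 2 | 2.0 |
| 120 mL | 5 | 3 | 3 | 1.67 |
| 150 mL | 6 | 4 | 3 | 2.0 |

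For V from 50 to 300 mL the ratio for 25 against 50 mL lies between 1.5 and 2.0. It cannot exceed 2, because V/25 rounded up is at most twice V/50 rounded up. For 25 against 40 mL it lies between 1.0 and 2.0; a 50 mL dose still needs two sites at 40 mL, so nothing is masked there.

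**Step 2: event rate.** If reactions at separate sites are separate events, the rate per infusion is n × r, with r the rate per site. The per-infusion rate is unchanged when r(50)/r(25) = n(25)/n(50), that is 1.5 to 2.0. Example with assumed rates and V = 50 mL: 2 × 0.10 = 0.20 at 25 mL, and 1 × 0.20 = 0.20 at 50 mL. With r unchanged at 0.10, the rate at 50 mL would be 0.10, half the 25 mL figure.

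**Step 3: tolerability.** With independent sites and per-site severe risk q, tolerability is (1 − q)^n. Going from 2 sites to 1 with q doubled:

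| q at 25 mL | Tolerability, 25 mL | Tolerability, 50 mL (q doubled) | Rise in q that leaves tolerability equal |
|---|---|---|---|
| 1% | 98.01% | 98.00% | 1.99-fold |
| 5% | 90.25% | 90.00% | 1.95-fold |
| 10% | 81.00% | 80.00% | 1.90-fold |

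From 3 sites to 2 the last column is about 1.5 (1.496 at q = 1%, 1.462 at q = 10%).

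**Step 4: what shrinks the effect.** A valid infusion needs only one site at 95% or more of the planned volume (Protocol Table 6), so more than the minimum may be used. A 100 mL dose given through 3 sites at the 50 mL level has a ratio of 4/3 = 1.33 instead of 2. If reactions at several sites are recorded as one event, the event rate behaves like tolerability in Step 3. If, in addition, a subject's sites always react together, the per-infusion rate equals the per-site risk and nothing is masked.

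**The case against.** **The per-infusion rate is what was prespecified, and it is not wrong.** For a fixed dose it tells the patient what to expect from each infusion, and fewer sites is part of the intervention. Severity is graded by its effect on the person's daily activities, not by site. This stands. A reader might infer that the SAP formula is biased; the documents do not support that. It answers a different question from the per-site one.

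**Infusions are not the only base reported.** Subject percentages and event counts are tabulated too. True, but neither is per site.

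**The label rule does not use these rates.** The new top level is the highest with a responder rate of at least 33% (Protocol 11.3.5, SAP 11.1), and response rests on valid infusions. This also stands: a reader might infer that the recommended level could be wrong because of the denominator, and that does not follow.

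**A per-site rate can mislead in its turn.** SAP 11.4 lists no injection-site identifier among the AE listing variables, and the documents do not say how a reaction at several sites is recorded. Suppose both sites at 25 mL always react together, with risk 0.10, and this is recorded as one event. The per-site rate is then 0.10 / 2 = 0.05 at 25 mL, against 0.10 at one 50 mL site: an artificial doubling. This is a good reason for a counting rule and for showing both rates, not for leaving site counts out.

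**Severe reactions will be few.** Protocol 1.4 reports 99% of earlier adverse events as mild or moderate, and 15 subjects × 4 infusions is about 60 infusions per level. The severe per-site rate will be imprecise; the rate for all local reactions is the more informative one.

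**The synopsis wording.** It might be read as promising a per-site analysis. The same synopsis defines its endpoints per infusion, so loose wording is more likely.

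**Conclusion.** The point holds as an omission, confined to the Pump-Assisted Volume Cohort; raising the flow rate does not by itself change the number of sites. From 25 to 50 mL per site, a 1.5- to 2-fold rise in per-site event risk, depending on weekly volume, could leave the per-infusion rate unchanged. Tolerability could conceal nearly as much when severe reactions are rare. These are upper bounds: they assume the minimum number of sites, separately counted reactions (for event rates) and independent sites (for tolerability). Actual site counts are not given, which is itself a reason to tabulate them. The documents do not show that per-site risk rises, only that the planned tables could not tell. The primary responder endpoint, the 33% criterion and the label rule are untouched. This is a cheap improvement, not a defect in the prespecified endpoints.

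**What to change.** Keep the per-infusion endpoints as they are. For the Pump-Assisted Volume Cohort, add by volume level:

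- in SAP 11.3, the number of injection sites per infusion;
- in SAP 11.4, supplementary rates of local reactions and of severe local reactions per injection site (events divided by total sites used at that level);
- in SAP 11.4, a rule for counting a reaction that covers several sites in one infusion. If the AE record does not show how many sites were affected, say that the numerator is AE records and that the rate may understate per-site risk where more sites are used.

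Interpret differences between volume levels with the per-infusion and per-site rates side by side. Reconcile the synopsis wording on rates with Protocol 11.3.3 and SAP 11.4.

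**Cost.** One extra table and the counting rule. The denominator can come from data already collected: volume and infusion location in the eDiary (Protocol 9.7.1) and catheter type (SAP 8.2.8). No change to visits, procedures or sample size is needed. The local-reaction profile at the higher volumes may look less favourable.

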11.3.3 Safety Analyses

AEs, laboratory, and vital signs will be summarized descriptively only within each of the 3 cohorts separately. No analysis combining data from 3 separate cohorts or comparing safety outcomes between cohorts will be performed.

If a subject is a non-responder at a certain infusion parameter level, AEs reported at the individually tolerable infusion parameter level after the non-response in the subject, ie, AEs starting at or after the next infusion following the infusion leading to non-response, will be listed and flagged, and analysed separately from the AEs reported prior to that time.

AEs will be summarized by the values of infusion parameters within each cohort. Rates per infusion will be presented as well. Adverse events will be presented including a virtual System Organ Class comprising local reaction (identified by the Medical Dictionary for Regulatory Activities high level terms: “administration site reactions NEC”, “infusion site reactions”, and “injection site reactions”) and by severity. Further, time to onset and duration will be presented descriptively. Tolerability of a certain infusion parameter within a cohort will be calculated as ‘number of infusions without severe local reaction / number of all infusions’ and be presented by infusion parameter and cohort. All infusions, regardless of the validity of the procedure (see Section 11.3.5) will be considered.

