3	12	7																				
4	16	10																				
5	20	12																				
6	24	15																				
7	28	17																				

Item	Definition
Success Criterion	Percentage responder for infusion parameter $p$ in cohort $c$ $R_{c,p}(\%) = \frac{100 * (\text{Number of responder for } p \text{ in cohort } c)}{\text{Number of subjects in the SAF for cohort } c}$ with the success criterion for any $R_{c,p}$ being fulfilled if $R_{c,p} \geq 33\%$ .
Start Date of Non-Response	Date of the next infusion after a subject was classified as non-responder.
Terms	
AE Rate per Infusion	Number of Adverse Events for a Particular PT / Number of Infusions Within Cohort
Baseline	Most recent non-missing value prior to or on the first study treatment dose date
Body Mass Index (kg/m  )	Body weight (kg) / Height (m) 
Compliance per Infusion (%)	(Actual amount per infusion/prescribed or planned amount per infusion)*100, where amount is dose (mg/kg) or volume (mL)
Duration of Event	End date of the event – start date of the event + 1
Elapsed Time Until Event	Event date – reference date
Local TEAEs	TEAEs identified by MedDRA high level terms “administration site reactions NEC”, “infusion site reactions”, and “injection site reactions”
Tolerability of an Infusion Parameter Within Cohort	Number of infusions without severe local reactions within cohort / number of infusions within cohort (irrespective of their validity); an infusion without severe local reactions is defined as no occurrence of a severe local reaction from the start date and time of an infusion until the start date and time of the next infusion or study end if this was the last infusion.
Treatment-Emergent	Event which started on or after the date (and time) of first administration of study treatment

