## 4 Study Design

### 4.1 Study Design

This multicenter, open-label, parallel-arm, non-randomized study is designed to evaluate safety and tolerability of higher infusion parameters of IgPro20 in subjects with primary immunodeficiency (PID). A target of 45 evaluable subjects (i.e., 15 subjects per cohort) is needed. Enrolled subjects will include a target of 14 (30%) pediatric subjects  $\leq 17$  years of age and a target of 9 (20%) obese subjects with body mass index (BMI) of  $\geq 30$  kg/m^2.

Pediatric and obese subjects may be distributed across any or all of the treatment cohorts without respect to balanced enrollment within the cohorts for these subpopulations..

Assignment to one of the cohorts will take place at the Screening visit and subjects cannot be

changed later to another cohort. The study will include 3 cohorts with a minimum of 15 subjects each as follows:

- Pump-Assisted Volume Cohort (weekly infusions): Volume per injection site of 25 mL up to 50 mL;
- Pump-Assisted Flow Rate Cohort (weekly infusions): Flow rate per injection site of 25 mL/hour (h) up to 100 mL/h
- Manual Push Flow Rate Cohort (2 to 7 infusions per week): Flow rate per injection site of 25 to 30 mL/h up to 120 mL/h (equivalent of approximately 0.5 mL/minute up to 2 mL/minute)

Each cohort will test 3 infusion parameter levels (for Pump-Assisted Flow Rate Cohort – 4 levels) for at least 4 weeks each over a duration of 12 weeks (for Pump-Assisted Flow Rate Cohort – 16 weeks). After the fourth week on each level, subjects may switch to the next infusion parameter level, if the current level has been tolerated (e.g., from 25 to 50 mL/h). During the study the weekly dose will remain unchanged (as prescribed by treating healthcare provider, usually within 100-200 mg/kg per week range); only the respective infusion parameter under evaluation will change. If a subject is unable to tolerate the respective infusion parameter level (i.e., is a non-responder at that level, for definition see Section 11.2), the subject will continue study participation at the individually previously tolerated infusion parameter level for the remaining full study duration, to collect safety information.

The final analysis to support the CSR will take place after all subjects have completed or terminated the study.

The schedule of assessments planned for the study can be found in the protocol.

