## 11.2 Non-Responder

If a subject is unable to tolerate a certain infusion parameter level (i.e., is a non-responder at that level), the subject will continue study participation at the highest individually tolerable infusion parameter level for the remaining full study duration to collect safety information.

If a subject is a non-responder at a certain infusion parameter level, data collected until the time of non-response will be taken into account for the analysis of response. Data collected at the individually tolerable infusion parameter level after the non-response in the subjects will not be included in the analysis of response but will be listed and flagged in the listing.

The start date of non-response is the start date of the next infusion after the subject has been classified as non-responder. If a subject is a non-responder at the last infusion parameter level, the start date of non-response will be missing as no further data will be collected after the last infusion parameter level.

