### 11.3 Extent of Exposure

Actual dose in mg/kg will be taken as entered in the database. For the Manual Push Flow Rate Cohort, the planned weekly volume will be derived from the planned weekly dose as entered in the eCRF assuming the nominal IgG content of IgPro20 being 200 mg/mL:

planned volume (mL) = planned dose (mg/kg) \* body weight (kg) / 200 mg/mL.

Subject's duration of exposure (days) in each infusion parameter level will be calculated as

(minimum of (treatment end date in parameter level [i] + 7 days, treatment start date in parameter level [i+1] – 1 day, study completion date) – treatment start date in parameter level [i]) + 1.

Subject's overall duration of exposure (days) will be calculated as

study completion date – date of first treatment + 1.

Duration in weeks will be derived by dividing the above item by 7.

Descriptive statistics for duration of exposure in weeks for each infusion parameter level and overall will be presented. In addition, the subject-years of exposure for each infusion parameter level and cohort will be given.

Subject's prescribed and actual dose (mg/kg) and total planned and actual volume (mL) per week will be summarized descriptively by cohort and infusion parameter level.

Number and percentage of incomplete infusions or infusions stopped will be presented. The base for the percentage will be the total number of infusions within the cohort.

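### SAP 11.4 splits AEs at non-response but states no matching split for infusions; read literally, per-infusion AE rates are too low at levels that subjects step back to

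*SAP*

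**What the plan says.** **Step-back.** Under SAP 4.1, when a level is not tolerated, "the subject will continue study participation at the individually previously tolerated infusion parameter level for the remaining full study duration". Protocol 3.1 says the same. Infusions at the lower level after a failure are therefore part of the design.

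**AEs.** For events that begin from the infusion after the one that led to non-response, SAP 11.4 says: "These AEs will be analyzed separately from the AEs reported prior to that time". Protocol 11.3.3 has the same rule ("analysed separately from the AEs reported prior to that time").

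**Infusions.** For the by-level rate, SAP 11.4 says that the "number of infusions will be the sum of all infusions that subjects received within infusion parameter level irrespective of their validity". The short definition in SAP 2.2 is "Number of Adverse Events for a Particular PT / Number of Infusions Within Cohort". Neither mentions non-response, and no second denominator is given for the AEs that are set apart.

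**Total.** SAP 11.4 adds: "In the Total column within cohort, each subject will only be counted once with all events experienced".

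**Cut date.** SAP 11.2 already defines one: "The start date of non-response is the start date of the next infusion after the subject has been classified as non-responder". It is missing for a subject who fails only at the last level, because no data follow that level.

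AE and local-reaction rates per infusion, by level, are secondary endpoints (Protocol 2.2.2, SAP 4.2).

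**The concern.** A rate per infusion is interpretable only if its events and its infusions come from the same period. SAP 11.4 states a time cut for the events and none for the infusions. Taken at its word, an infusion given at 25 mL/h after failure at 50 mL/h counts in the 25 mL/h denominator, while an AE that follows it does not count in the 25 mL/h numerator.

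Only levels that receive step-back subjects can be diluted, and the top level never does. A flat true rate could then appear to rise with volume or flow rate, in a study whose purpose is to describe tolerability as those parameters increase. The level columns would also fail to add up to a Total column that holds every event.

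**Working it through.** The plan states no figure for AE rates or for the number of step-backs, so there is none to reproduce. Its 94% (SAP 4.5) concerns the responder count and does not enter here; the binomial tail P(X ≥ 5; n = 15, p = 0.5) = 0.9408 does reproduce it.

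**Inputs from the documents**
- 15 subjects per cohort (SAP 4.5).
- Four weeks per level, over 12 weeks, or 16 in the pump flow rate cohort (SAP 4.1).
- Weekly infusions in the pump cohorts, so 15 × 4 = 60 infusions at level 1.

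**Assumptions**
- How many subjects step back, and where.
- Step-back happens after the four weeks at the failed level. If it happens sooner, more step-back infusions accrue and the effect is larger.
- Everyone tolerates level 1, and nobody drops out.

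**Formula.** Let E_pre and I_pre be AEs and infusions at a level before non-response, and I_post the step-back infusions at that level.
- Matched rate = E_pre / I_pre
- Literal rate = E_pre / (I_pre + I_post)
- Literal / matched = I_pre / (I_pre + I_post)

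The ratio does not depend on the AE rate during step-back. It needs only that E_pre is not zero.

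**Level 1, by number of subjects failing level 2.** Each adds 4 step-back infusions in a three-level cohort (weeks 9–12) and 8 in the flow cohort (weeks 9–16).

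| Failing level 2 | Three-level cohort | Flow cohort |
|---|---|---|
| 0 | 60/60 = 1.00 (0%) | 60/60 = 1.00 (0%) |
| 1 | 60/64 = 0.938 (6% low) | 60/68 = 0.882 (12% low) |
| 3 | 60/72 = 0.833 (17% low) | 60/84 = 0.714 (29% low) |

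The three-level ratios also apply to manual push if infusion frequency is unrelated to failure, because the weekly frequency cancels.

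**What the table could look like.** Flow cohort, two subjects failing 50 mL/h and two failing 75 mL/h, with an illustrative flat true rate of 0.50 AEs per infusion, step-back infusions included.

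| Level | I_pre | I_post | E_pre | Literal rate |
|---|---|---|---|---|
| 25 mL/h | 60 | 2 × 8 = 16 | 30 | 30/76 = 0.39 |
| 50 mL/h | 60 | 2 × 4 = 8 | 30 | 30/68 = 0.44 |
| 75 mL/h | 13 × 4 = 52 | 0 | 26 | 26/52 = 0.50 |
| 100 mL/h | 11 × 4 = 44 | 0 | 22 | 22/44 = 0.50 |

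Infusions sum to 216 + 24 = 240 = 15 × 16. Events in the level columns sum to 30 + 30 + 26 + 22 = 108. The step-back infusions contribute 24 × 0.50 = 12 more, so Total is 120/240 = 0.50. A flat rate is displayed as a rising one, and 12 events sit in Total but in no level column.

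**The case against.** **The main tables may keep every AE.** SAP 11.4 never says in terms that post-non-response AEs leave the by-level tables. By contrast, SAP 11.2 does say that step-back data are left out of the response analysis. SAP 7 and 11.4 assign each event to the level where it occurred, and Total holds all events. If the listed tables keep all TEAEs and the separate analysis is additional, the rate is (E_pre + E_post)/(I_pre + I_post), where E_post is the step-back AEs, and there is no bias. This is a real alternative and the shells could confirm it. It does not sit well with the instruction, in both documents, to analyse those AEs apart from the earlier ones.

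**The denominator may already be matched.** SAP 11.3 ends time in a level the day before the next level starts, so infusions within a level might be read in the same way. But 11.3 defines days of exposure, 11.4 gives its own rule that counts all infusions received, and neither refers to the other. The remark on validity settles whether invalid infusions count; it does not remove step-back infusions.

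**The size is assumed.** This stands. The documents give no step-back count, and the plan expects no infusion-related reasons for changing parameters (SAP 11.1).

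**The consequence is limited.** This also stands. The analysis is descriptive, subject and event counts appear beside each rate, and post-non-response data are flagged in the listings, so a matched rate can be rebuilt.

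**Conclusion.** The gap is real and the conclusion is conditional. The SAP gives a cut for AEs and none for infusions. Followed literally, that understates per-infusion AE and local-reaction rates at step-back levels by the factor pre/(pre + post). On the stated assumptions the level 1 rate is 6% to 17% too low in the three-level cohorts, and 12% to 29% too low in the flow cohort, for one to three of 15 subjects failing level 2. It is not affected if nobody steps back or if failures occur only at the top level.

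A reader might infer more, and the documents do not support it:
- **That the reported rates will be biased.** A matched reading exists and the shells are not available.
- **That AEs are lost.** They are listed, flagged and analysed separately; what is missing is a denominator for that analysis.
- **That the higher levels are made to look safer.** The error runs the other way. It lowers only the lower levels, so the higher ones look worse by comparison.
- **That the label decision is at risk.** The primary endpoint and the 33% criterion do not use these rates. Tolerability is counted infusion by infusion, so its numerator and denominator cover the same infusions.

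**What to change.** In SAP 11.4, use the start date of non-response from Section 11.2 to split both AEs and infusions:
- By-level rates use AEs and infusions before that date, or all infusions if the date is missing.
- AEs from that date onward are divided by infusions from that date onward, by level actually infused, in a separate column or display within the same table.
- Total stays as all events over all infusions.

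The level columns plus the post-non-response column then reconcile with Total. In the flow example this gives 108/216 and 12/24, which together make 120/240, and every level shows 0.50.

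The cost is a short SAP amendment, a little extra programming and one more column or display. Infusion dates and the non-response date are already derived, so no new data are needed and study conduct does not change.

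Optionally, and apart from the rate error, SAP 11.3 could add a row for exposure after non-response, since its formula assigns step-back time to no level.
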